A limiting factor in the use of epidural analgesia, however, is the high incidence of associated hypotension. Hypotension is defined as systolic blood pressure (SBP) > 20% below the baseline preoperative measurements and acquired before the epidural or any sedation has been administered. Effective segmental epidural block would thus invariably cause sympathectomy due to its location in the thoracic or lumbar areas by blocking the cardiac sympathetic nerves, the pre-ganglionic nerves to the adrenal glands or the sympathetic nerves to the blood vessels individually or in combination.

It has been proven beyond doubt that epinephrine, when added to ropivacaine 0.2% and used for epidural analgesia by infusion, is safe and may even improve spinal cord blood flow and the analgesic effects of ropivacaine.⁷ It is also known that the cause of hypotension associated with epidural analgesia is the blockade of the sympathetic outflow to the cardiovascular and adrenal systems, and that the ideal mechanism to counter this would be by beta1-stimulation, which is ideally achieved with low-dose epinephrine.

Finally, it is known that epidural infused epinephrine increases its serum concentration.⁸ What is not known is whether added epinephrine will counteract this sympathetic blockade and prevent hypotension, and what the optimal concentration of epinephrine infusion would be during epidural analgesia with 0.2% ropivacaine to achieve optimal analgesia and optimal hemodynamic status.

5. Specific Aims:

We aim to examine whether adding epinephrine will counteract the sympathetic blockade and prevent hypotension, and what the optimal concentration of epinephrine infusion would be during epidural analgesia with 0.2% ropivacaine that can achieve both optimal analgesia and optimal hemodynamics. Specifically we plan to answer the following questions:

- 1. Does the addition of epinephrine to the epidural infusion of 0.2% ropivacaine:
 - a. Prevent hypotension?
 - b. Lead to a wider spread of local anesthetic effect?
 - c. Lead to a difference in the average pain scores?
 - d. Lead to a difference in when ambulation occurs?
 - e. Decrease potential of other opioid-related side effects such as pruritus, nausea/vomiting, respiratory depression and opioid consumption?
- 2. What is the optimal concentration of epinephrine (2mcg/mL or 5mcg/mL) to achieving the above-mentioned outcomes?

6. Research Plan:

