Primary measurements:

Include the average invasively or non-invasively measured SBP, diastolic blood pressure (DBP), MAP, arterial blood oxygen saturation (SaO2), heart rate, respiratory rate, and pain by the visual analog pain score (VAS) on the "Defense and Veterans Pain Rating Scale" (DVPRS) measured over the following set periods:

Preoperative period

Primary measurements every 3 to 5 minutes and at indicated time points:

- I. Before the bolus epidural is injected.
- II. After the epidural bolus is injected but before anesthesia is induced.

Intraoperative period

Primary measurements every 3 to 5 minutes

Postoperative period

I. Primary measurements in the recovery room (if appropriate) every 15 minutes

II. Primary measurements following transfer to the floor every 4-6 hours if within normal limits, but every hour if needed for closer observation in case of possible abnormality for as long as the epidural analgesic blocks are continued, but at least every 8 hours after discharge from the PACU.

Secondary measurements:

[figure not shown]
- III. Spread of block per spinal root segment as tested by sensitivity to cold recorded every hour postoperatively and every 8 hours for the subsequent 72 hours after discharge from the PACU.
- IV. Ambulation on the first day after surgery (POD 1), POD 2 and 3, will be recorded per physical therapy protocol and distance ambulated per 24hour period will also be recorded. Physical Therapy information will be gathered to test motor effect on lumbar epidurals.
- V. Opioid usage data will be recorded and converted to morphine equivalents and averaged for POD 0, 1, 2, and 3 per group.
- VI. Side effects such as pruritus, nausea/vomiting, and respiratory depression (defined as respiratory rate less than 10 breaths per minute of oxygen saturation more than 7 points lower that the patients preoperative value on room air) will be recorded and managed as deemed appropriate by the attending physician.
- VII. 24 hour I/O for the first 72 hours to assess fluid balance, length of stay, and amount of days before return to PO status.

Data analysis plan

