All data will be entered securely using the online database or Red Cap. To assess potential dose-response effects on changes in continuously measured primary outcomes, repeated measures mixed modeling analyses will be used. This type of analysis can assess the main effects of time (i.e., change) and group (i.e., epinephrine dose; coded as an ordinal variable) on the outcomes. Mixed models are the preferred approach to analyze data with repeated measures; these models can account for correlation among repeated measurements, flexible time effects, and can handle missing data. Additionally, this model can estimate time × group interactions. If this interaction is statistically significant, that provides evidence that the changes in outcomes are different depending on the dose of epinephrine that a patient received. Logistic regression models will be used to assess the relationship between epinephrine dose and incidence of hypotension (SBP < 20% or MAP < 55 mmHg) and other categorical outcome variables. A P value of <0.05 was considered statistically significant for all statistical tests. All analyses were conducted in JMP Pro 11.0 (SAS Institute, Cary, NC).

Sample size determination

At 80% power (alpha = 0.05), a sample of n=200 (50 per group) will be able to detect 26% differences in incidence of categorical outcomes, and an effect size of Cohen's f = 0.24 for group mean differences and effect size of Cohen's f = 0.09 for group differences mean change over time. Figure 1 depicts how these effect sizes will translate to the outcomes, with assumed standard deviations in outcomes ranging from 5 to 25. For example, assuming MAP has an SD = 10, the present study will be able to detect mean differences of 5 mmHg across groups and group differences of 3 mmHg for mean change over time.

ADMINISTRATIVE RESPONSIBILITIES:

Study Resources: The principal investigator will oversee the data collection, data analysis and will maintain the records in confidence. Should any evidence suggest that the study protocol require modification, the PI will notify the IRB in a timely manner for review and approval. Each subject will be identified by number, not by name, on all data forms. To protect confidentiality, all data will be numerically coded and information linking the numeric codes to individual participant's names will be kept in a locked file in the PI's office.

7. Possible Discomforts and Risks:

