Regional anesthesia - The risks of regional anesthesia include, but are not limited to low blood pressure, allergic reaction to drugs, obstruction or cessation of breathing, headache, paralysis, nerve injury, bleeding, blood clots, infection or meningitis, falls after surgery, drug reactions (including rash, shock, and cardiac/respiratory arrest), stroke or brain injury, heart failure or heart attack, and death. The epidural would be immediately turned off if the patient were to have unwanted side effects such as uncontrolled increase in heart rate or blood pressure, arrhythmias, anxiety, or unwanted clinical symptoms that could be attributed to the epinephrine dose in the epidural. The pharmacy would immediately be contacted to determine the epinephrine dose in the patient's epidural so that clinical treatment be tailored appropriately.

The PI will oversee the data collection, data analysis, and will maintain the records in confidence. The data collected will be stored in a secure, password protected database with strong encryption, on a computer server, accessible only by the study team. Any additional digital data files from the study will be de-identified and stored on a password protected laptop computer. Hence, encryption will be required. All paper records will be stored in locked file cabinet in the PI's locked office. The patient consent forms will be the only documentation with PHI. The results collected and calculated by the laptop software will be non-PHI data including the patient demographics, administration amounts of drugs, the time of those administrations, and the post-operative times to emergence and the occurrence of respiratory depression.

8. Possible Benefits:

It has been proven beyond doubt that epinephrine, when added to ropivacaine 0.2% and used for epidural analgesia by infusion, is safe and may even improve spinal cord blood flow and the analgesic effects of ropivacaine.⁷ Because of this, the possible benefit to the participant is to improve the effects of the epidural anesthesia and to reduce the possible sympathetic side effects.

9. Conflict of Interest:

None of the investigators have a conflict of interest.

References

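### Epinephrine-attributed events and the epidural turn-offs they trigger are not prespecified outcomes by arm, and Aim 2 names no epinephrine harm to weigh when choosing the optimal concentration

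*Combined protocol and SAP*

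**What the plan says.** **Choice of dose.** Section 5 (Specific Aims) seeks a concentration "that can achieve both optimal analgesia and optimal hemodynamics", without defining the hemodynamic part. Aim 2 asks: "What is the optimal concentration of epinephrine (2mcg/mL or 5mcg/mL) to achieving the above-mentioned outcomes". Those outcomes are Aims 1a to 1e: hypotension, spread of block, pain, ambulation, and opioid-related side effects with opioid consumption.

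**Stops.** Section 7 (Possible Discomforts and Risks) says: "The epidural would be immediately turned off if the patient were to have unwanted side effects". It describes these as "unwanted side effects such as uncontrolled increase in heart rate or blood pressure, arrhythmias, anxiety, or unwanted clinical symptoms" attributable to the epinephrine. It does not say how the patient's data are then analysed.

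**Data.** In Section 6, the primary measurements are averages over set periods and include systolic, diastolic and mean pressure and heart rate. Ward readings run "for as long as the epidural analgesic blocks are continued", and the same sentence adds a minimum eight-hourly frequency after recovery-room discharge. Item VI of the secondary measurements reads "Side effects such as pruritus, nausea/vomiting, and respiratory depression".

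**Analysis.** The Data analysis plan uses mixed models by dose and time for continuous outcomes. Logistic regression is to "assess the relationship between epinephrine dose and incidence of hypotension" and to handle other categorical outcomes, which are not named.

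**The concern.** A dose-finding comparison needs both sides of the dose-response. The protocol itself names the effects serious enough to end the study infusion, yet plans no comparison of them between arms. Aim 2 could therefore be answered in favour of a concentration without any reader seeing how often that concentration had to be stopped.

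There is a second route to trouble. Section 4 (Background) attributes the hypotension to the sympathetic block. Turning the epidural off removes the cause of the hypotension along with the study drug. If stopping depends on dose, the arm stopped more often may record less hypotension for that reason alone, or may lose patients from the comparison.

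**Working it through.** **1. The plan's own figures.** The Sample size determination gives 200 patients, 50 per group, 80% power, alpha 0.05 (taken as two-sided), a detectable f of 0.24 and a 26-point difference in categorical outcomes.
- Four groups, noncentrality f²N = 0.24² × 200 = 11.52 on 3 and 196 degrees of freedom: power 81.5%. The detectable f at 80% power is 0.236. This agrees.
- Two proportions: power = Φ{[d√n − 1.96√(2p̄(1−p̄))] / √(p₁(1−p₁) + p₂(1−p₂))}, where d is the difference and p̄ the mean of the two rates. For 20% vs 46% at n = 50: (1.838 − 1.303)/0.639 = 0.837, power 79.9%. This agrees, at an assumed base rate of 20%.

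These figures are not in dispute. They set the scale for what follows.

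**2. Events that stop the infusion, set against planned data.**

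| Section 7 event | Planned measurement | Planned comparison by arm |
|---|---|---|
| Rise in heart rate or blood pressure | Primary, averaged | Mean and change; no upper threshold |
| Arrhythmia | Not listed as an outcome | None named |
| Anxiety | Not listed as an outcome | None named |
| Turn-off for any of these | Not listed as an outcome | None named |

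**3. Dilution by averaging (assumed readings).** Three hours at five-minute intervals gives 36 values. Three at 140 and 33 at 70 average (3 × 140 + 33 × 70)/36 = 2,730/36 = 75.8. The episode moves the period mean by about 6 beats.

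**4. Could stops change the ordering? (All rates assumed.)** Let h be hypotension and s the stop rate. If stops and hypotension do not overlap, 5 mcg/mL (C) does worse than 2 mcg/mL (B) on the sum when s_C − s_B > h_B − h_C. Take h = 40/25/20% in A/B/C, a gain of 5 points for C over B.
- Stops 0/2/10%: sums 40/27/30%. The excess of 8 points is larger than 5, so B is lower.
- Stops 0/2/5%: sums 40/27/25%. The excess of 3 points is smaller than 5, so C stays lower.
- With independent overlap, 1 − (1−h)(1−s): 40/26.5/28% and 40/26.5/24%. The conclusions are the same.

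**5. Hypotension hidden by stopping (assumed).** If a share s is stopped while still free of hypotension, and a share q of those would have become hypotensive had the infusion continued, recorded incidence falls by s × q. With q = 25%, stops of 10% and 2% hide 2.5 and 0.5 points, a net shift of 2 points. The shift within an arm cannot exceed s.

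**6. What the trial could show about stops (assumed rates, two-sided 0.05).**

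| Control vs 5 mcg/mL | Power, 50 per arm | Power, 66 per arm | n per arm for 80% |
|---|---|---|---|
| 2% vs 6% | 17% | 21% | 376 |
| 2% vs 10% | 39% | 49% | 138 |
| 2% vs 15% | 65% | 77% | 72 |
| 2% vs 20% | 83% | 92% | 47 |

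The 66 column splits 200 over the three groups that the protocol lists. For 4/50 vs 0/50, Fisher's two-sided p = 2 × C(50,4)/C(100,4) = 2 × 230,300/3,921,225 = 0.12. Zero events in 50 gives a one-sided 95% upper bound of 1 − 0.05^(1/50) = 5.8%.

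**The case against.** The other side has substance, and several stronger readings that a reader might infer do not survive it.

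- **That epinephrine's effects go unmeasured.** Not so. Heart rate and blood pressure are primary measurements, taken every 3 to 5 minutes before and during surgery and modelled by dose. A sustained rise would be visible. The gap is in brief episodes, arrhythmia, anxiety and stops.
- **That Aim 2 can only reward more epinephrine.** Aims 1c and 1d ask about a difference, with no direction. A stop also ends the epidural analgesia, so pain, opioid use and ambulation could worsen in an arm stopped often. What holds is narrower: none of these outcomes measures an epinephrine harm.
- **That readings cease at the stop and the patient counts as free of hypotension.** The ward sentence continues with an eight-hourly minimum that can be read as applying whether or not the block runs. Nothing says how a stopped patient is classified, and hypotension before the stop would remain an event. The plan is silent on this point. The Intraoperative subsection removes patients after certain other turn-offs, which makes the silence worth resolving.
- **That 5 mcg/mL would be declared best while being stopped most.** The plan ranks no point estimates, only tests at 0.05, and gives no stop rate. Gaps of a few points are far below its 26-point detectable difference.

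It is also fair to say that item VI is an open list, that pain service records are scheduled through the third postoperative day, that drug amounts and times are kept, and that 5 mcg/mL is already one of two routine infusions at the institution. Stop times may therefore be recoverable. None of this prespecifies the reason for a stop or a comparison by arm.

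**Conclusion.** The point holds as a gap in prespecification. The events that end the study infusion, and the stops themselves, are not outcomes by arm, and Aim 2 says nothing about how harm bears on the choice. A distortion of the hypotension comparison is possible. At the assumed stop rates of 10% and 2% it is about 2 points, so the omitted harm matters more than the hidden hypotension. A reversed ordering needs an excess of stops larger than the hypotension gain, and the documents neither show this nor rule it out.

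Every rate used here for hypotension and for stops is assumed. The conclusion also assumes that the figure at the head of the secondary list, which I could not see, holds no further outcome. The numbering from III appears to continue the postoperative list, so this is likely.

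**What to change.** 1. Add to the secondary measurements: epidural turned off for an effect attributed to epinephrine, with reason and time.
2. Add the incidence of high heart rate and of high blood pressure from readings already taken, with analysis thresholds set by the investigators before unblinding.
3. Report these, with the other Section 7 events, by randomised arm with confidence intervals.
4. State that stopped patients stay in the hypotension analysis in their randomised arm, using the readings that continue, and clarify that the eight-hourly minimum applies after a stop.
5. State that the Aim 2 conclusion considers these events alongside hypotension.

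A composite of hypotension or epinephrine-related turn-off is at most an optional sensitivity analysis.

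The cost is one form field, a few tables and some protocol wording. With few events the comparison will be mainly descriptive and should be labelled so. No treatment or stopping rule changes.
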